For patients who lack the capacity to consent, the investigator/designee may explain the study to the legally authorized representative by phone. The discussion will be documented in the subject's medical record or research chart. Two copies of the unsigned consent form will be sent to the subject/legal representative with instructions for completion of the signature page and assent (if applicable). Signatures will be obtained according to standard Baylor IRB regulations. The subject will be told to keep one form and returned the other to the investigator by mail, email, or fax. The Baylor Investigator/designee will sign the consent form when returned from the subject. The signed consent form will be maintained in research records.

E3. Pregnant woman/fetus

Will pregnant women and/or fetuses (as described in 45 CFR 46 Subpart B) be enrolled in the research?

No

E4. Neonates

Will neonates of uncertain viability or nonviable neonates (as described in 45 CFR 46 Subpart B) be enrolled in the research?

No

E5. Children

Will children be enrolled in the research?

No

Section F: Design/Procedure

F1. Design

Select one category that most adequately describes your research:

c) Pilot

Discuss the research design including but not limited to such issues as: probability of group assignment, potential for subject to be randomized to placebo group, use of control subjects, etc.

Phase I: 20 subjects with COVID-19 infection that are being treated in the hospital. This means that this patient population is positive to COVID-19, are hospitalized, or develop severe symptomatology, but they have been admitted with no more than 48 hours to the hospital. Also, in some cases the patients will not be able to consent at the time of enrollment determines a high grade of severity of illness. The entire cohort will receive daily electrical stimulation in lower extremity (e.g. Gastrocnemius, tibial anterior muscle) up to 1 hour to decrease Neuromyopathy complications and prolonged hospital stay. Due to the condition of the patient we are looking to reduce the interaction with staff, the device will be placed with no additional requirements. Physical therapy targets other physical performances, this device is aimed to improve blood flow, tissue perfusion and muscle activation while the patient is non-responsive to physical activities.

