Provide a description of your plan for data analysis. State the types of comparisons you plan (e.g. comparison of means, comparison of proportions, regressions, analysis of variance). Which is the PRIMARY comparison/analysis? How will the analyses proposed relate to the primary purposes of your study?

P-values of 0.05 or less will be considered statistically significant based on a two-sided test unless otherwise noted. All variables will be tabulated descriptively at each scheduled time point (baseline and discharge date). For each continuous variable, the analyses will include the mean, standard deviation, minimum and maximum. For each categorical variable, the summary will include frequencies and percentages. Each variable will be analyzed using all available data. Baseline variables will be summarized using descriptive statistics. We assume that a successful intervention is also helpful to maintain subjects muscle mass, reduce neuromyopathy signs and increase venous return flow. The measured parameters (e.g. muscle circumference, sEMG, kent imaging, doppler, etc.) should change substantially from baseline to the end of the intervention. For example, the EMG amplitude values should show increased voltages. Next, for all continuous variables, pre-treatment scores will be regressed on post-treatment scores to form residualized change scores (e.g. sEMG, VPT, dynamometer, etc). Correlations will then be generated among these scores to determine whether changes in sEMG factors are related appropriately with increases in (clinically assessed) functional capacities and self-report measures of activities. ANOVA test will be used to examine significant difference between patients with severe risk factors for prolonged ICU stage (e.g. age, BMI, cardiovascular morbidities). Moderator effects will also be examined for exploratory purposes. Using gender as an example, mixed design ANOVAs will be conducted to determine whether mobility factors change over

the course of treatment at different rates or with different patterns for men and women. Additional analyses will test whether changes in muscle strength and neuropathy (e.g. VPT and dynamometer assessment at time of discharge).

Section H: Potential Risks/Discomforts

H1. Potential Risks/Discomforts

Describe and assess any potential risks/discomforts; (physical, psychological, social, legal, or other) and assess the likelihood and seriousness of such risks:

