Describe potential benefit(s) to be gained by the individual subject as a result of participating in the planned work.

There is potential benefit of prevention or improvement of hospital acquired weakness due to prolonged hospital stay for participants, based on previous studies the electrical stimulation will improve blood flow, tissue perfusion and muscle activation. The device is used to reduce pain. However, the proposed treatment may assist in preventing or improving hospital-acquired Weakness because of prolonged hospital stay . In addition, the participation in this study may help the investigators better understand how COVID19 may impact cause myopathy and neuropathy and how to best help these patients to recover from prolonged hospital-stay .

Primary outcomes include neuropathy (assessed using VPT test); muscle function (assessed using sEMG), and tissue oxygenation (assessed using Kent Imaging). Secondary outcomes include weakness (assessed using dynamometer); muscle atrophy (assessed by weight loss as well as measuring ankle, calf, and thigh circumference); venous return flow (Doppler US [optional]); frailty (frailtymeter [optional]); hospital length of stay (patient medical record); and major adverse events (patient health record). The primary and secondary outcomes will be assessed at baseline (if feasible) and on biweekly basis up to 4 weeks or hospital discharge, whichever came first. Appropriate mixed models (linear for continuous or Generalized Estimating Equations (GEEs) for non-continuous or non-parametric variables) will be used to test the intervention effect for each of the primary (e.g., tissue perfusion, tissue oxygen delivery, neuropathy severity, and

myopathy incident) or secondary (e.g., frailty, weight loss, MAE, etc) outcomes.

Also, participation may help the investigators design a practical assessing method to identify the impact of neuromyopathy in the hospital setting. This may allow physicians to provide personalized care by monitoring muscle loss and limb complications caused by prolonged hospital length of stay.

Describe potential benefit(s) to society of the planned work.

As described above, this type of work may allow physicians to provide more personalized care for hospitalized patients in need of physical therapy for continuous and prolonged periods, specially when having a severe illness that includes medical staff risk contact.

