Title: Electrical Stimulation Therapy for Preventing Hospital-acquired Weakness in Critically Ill COVID-19 Patients - A Proof of Concept Randomized Controlled Trial

Identifier: NCT04685213

Date: May 21, 2021

Statistical analysis plan

Shapiro-Wilk test ($p > 0.05$) was used to assess the normality of data. Independent t-test was used for group comparison at baseline on normally distributed continuous demographics, clinical data, and sEMG parameters. Mann-Whitney U test was used if the assumption of normal distribution was not satisfied. For categorical variables, Chi-square test was used to compare between-group differences at baseline. The effect size for baseline continuous and categorical data were measured using Cramer's V and Cohen's d, respectively. Generalized estimating equations (GEE) was used to test the main effect of group (two levels: CG and IG), time (three levels: baseline, 3 days, and 9 days), and their interaction on the outcome measures regardless of data unable to obtain due to the patients' critical condition. Pearson correlation was used to associate baseline values with %change of outcomes at 9 days. For those significant associations, multiple linear regression was used to determine the relationship between those significantly associated variables. The model performance was reported in terms of variance (R^2), and p-value. For all tests, an alpha level of < 0.05 was considered statistically significant.

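### Protocol G2 builds its residualised change scores backwards (pre regressed on post), so the planned sEMG–function correlations would partly reflect baseline; the treatment-effect test is unaffected

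*Protocol*

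**What the plan says.** Protocol Section G2 (Data Analysis) states that, for all continuous variables, "pre-treatment scores will be regressed on post-treatment scores to form residualized change scores". It gives sEMG, VPT and dynamometer as examples. It goes on: "Correlations will then be generated among these scores to determine whether changes in sEMG factors are related appropriately" to increases in functional capacity and self-reported activity. The significance rule in the same section is: "P-values of 0.05 or less will be considered statistically significant based on a two-sided test unless otherwise noted".

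The treatment effect is handled separately. In Protocol Section I, mixed models or GEE "will be used to test the intervention effect for each of the primary" and secondary outcomes. In the SAP, "Generalized estimating equations (GEE) was used to test the main effect of group", time and their interaction. Neither uses residualised scores. The SAP has a different correlation analysis ("Pearson correlation was used to associate baseline values with %change of outcomes at 9 days") and does not mention the G2 step, either to keep it or to withdraw it.

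**The concern.** In standard usage, the variable that is regressed is the outcome and the variable it is regressed on is the predictor. G2 therefore makes the pre-treatment score the outcome and the post-treatment score the predictor. Residualised change needs the reverse, because its purpose is to remove baseline from the follow-up value.

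The residual described in G2 removes the follow-up value and leaves baseline in. Patients who enter weak on both sEMG and dynamometry could then produce an apparent link between sEMG change and functional change when no shared change exists. A real link could equally be diluted. What is at stake is the supportive claim that sEMG change tracks clinical function.

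**Working it through.** The plan gives no figure to reproduce here: G1 describes the sample size as one of convenience, and no power calculation or expected correlation is stated. The check is therefore algebra plus simulation over an assumed range.

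**Inputs from the documents.** Direction of regression, use of the scores, and two-sided 0.05: Protocol G2. Sample size: Phase I has "20 subjects with COVID-19 infection that are being treated in the hospital" (Protocol F1).

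**Assumed inputs.** For measures k = 1, 2, standardised baselines x1 and x2 have correlation b. Post-treatment is y_k = r_k x_k + sqrt(1 − r_k²) e_k, where r_k is the pre-post correlation and corr(e1, e2) = q is the correlation of baseline-adjusted change. There are no cross-lagged effects.

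**Step 1, one score.** The residual as written is B_k = x_k − r_k y_k = (1 − r_k²) x_k − r_k sqrt(1 − r_k²) e_k.
- Variance: (1 − r²)² + r²(1 − r²) = 1 − r².
- Correlation with the post-treatment value: 0.
- Correlation with baseline: (1 − r²)/sqrt(1 − r²) = sqrt(1 − r²), which is 0.95, 0.87, 0.60 and 0.44 for r = 0.3, 0.5, 0.8 and 0.9.
- Correlation with the proper residualised change score: −r.

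**Step 2, two scores.** The covariance of B1 and B2 is (1 − r1²)(1 − r2²) b + r1 r2 sqrt((1 − r1²)(1 − r2²)) q. Dividing by the two standard deviations gives

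corr(B1, B2) = sqrt((1 − r1²)(1 − r2²)) b + r1 r2 q.

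The proper direction gives q. With equal r the formula is (1 − r²) b + r² q. For example, r = 0.5, b = 0.5, q = 0 gives 0.75 × 0.5 = 0.375 where the target is 0. If q = b and r1 = r2, the two directions agree.

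**Step 3, simulation.** n = 20, regressions fitted within each sample, two-sided p ≤ 0.05, 40,000 samples per setting (3,000 for the last row).

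| r1, r2 | b | q (target) | As written: correlation | As written: significant | Proper direction: significant |
|---|---|---|---|---|---|
| 0.3, 0.3 | 0.5 | 0 | 0.455 | 49% | about 5% |
| 0.5, 0.5 | 0.5 | 0 | 0.375 | 34% | about 5% |
| 0.8, 0.8 | 0.5 | 0 | 0.180 | 10% | about 5% |
| 0.9, 0.9 | 0.5 | 0 | 0.095 | 6% | about 5% |
| 0.3, 0.3 | 0.3 | 0 | 0.273 | 20% | about 5% |
| 0.5, 0.5 | 0.3 | 0 | 0.225 | 14% | about 5% |
| 0.8, 0.8 | 0.3 | 0 | 0.108 | 7% | about 5% |
| 0.9, 0.9 | 0.3 | 0 | 0.057 | 5% | about 5% |
| 0.5, 0.8 | 0.5 | 0 | 0.260 | 17% | about 5% |
| 0.3, 0.8 | 0.5 | 0 | 0.286 | 19% | about 5% |
| 0.8, 0.8 | 0.5 | 0.3 | 0.372 | 34% | 24% |
| 0.8, 0.8 | 0.3 | 0.5 | 0.428 | 44% | 59% |
| 0.3, 0.8 | 0.5 | 0.5 | 0.406 | 39% | 60% |
| 0.5, 0.5 | 0.5 | 0.5 | 0.500 | 60% | 60% |
| 0.5, 0.5 | 0 | 0.5 | 0.125 | 7% | 60% |

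The correlations shown are population values from the formula. Simulated sample means are slightly lower (for example 0.242 against 0.260).

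**The case against.** **It is probably a transposition.** The sentence names residualised change as its product, and the next sentence speaks of change in sEMG. This stands as a likely explanation. It does not tell an analyst which regression to fit, and nothing in either document corrects the wording.

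**The SAP seems to have moved on.** It has its own correlation plan and is written in the past tense. This also stands in part, but silence is not withdrawal, so the protocol step is still nominally in force.

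**The large rates need a particular scenario.** Under the model, the post-treatment correlation of the two measures is r1 r2 b + sqrt((1 − r1²)(1 − r2²)) q. With b = 0.5 and q = 0 it falls from 0.5 at baseline to 0.25 × 0.5 = 0.125 (r = 0.5) or 0.09 × 0.5 = 0.045 (r = 0.3). With equal r, a stable cross-sectional association forces q = b, which is the case without distortion. This is correct and limits how much weight the 34% and 49% can bear.

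**The proper direction is not always clean.** If pre and post are equally noisy readings of unchanged traits, with r = 0.5 and baseline correlation 0.5, simulation gives a mean correlation of 0.16 and about 9% significant in both directions. That scenario breaks the no-cross-lag assumption. With independent errors it also requires perfectly correlated traits, since 0.5/sqrt(0.5 × 0.5) = 1. It shows that swapping the terms does not cure measurement error, but it does not justify the reversed regression.

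**Fewer than 20 patients may have paired data.** Section I makes baseline assessment conditional on feasibility, and the SAP acknowledges missing data. At n = 12, with b = 0.5 and q = 0, the rate is about 18% (r = 0.5) or 26–27% (r = 0.3). The illustration shrinks, but the reversal remains.

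**Conclusion.** The concern holds: the regression in G2 is the wrong way round as written, and that conclusion needs no assumption. Its effect depends on r, b and q, none of which the documents give. Under the stated model with n = 20, q = 0 and b between 0.3 and 0.5, false significance runs from about 5–6% at r = 0.9 to 20–49% at r = 0.3. The distortion is small when pre-post correlation is high, absent when q = b with equal r, and it can also hide a real association. None of this predicts that reversed scores would actually be computed. The severity is minor: one supportive correlation analysis is affected, and the tests of the intervention effect in Protocol Section I and the SAP do not use these scores.

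**What to change.** Reword the G2 sentence so that post-treatment scores are the outcome, pre-treatment scores are the predictor, and the residuals from that regression are the residualised change scores. Alternatively, if the SAP's correlation analysis is meant to replace this step, say explicitly in the protocol that it is withdrawn. Either way the change is one sentence. It needs no new data, visits or patients, and the treatment-effect analysis stays as it is.

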Aim 2 (to examine effectiveness): Examine effectiveness of daily use of EE to treat CINM, and other associated major adverse events (MAE) including deep vein thrombosis (DVT), cardiovascular events, and death. Participants will receive standard of care plus adjunctive daily EE therapy using an FDA approved bio-electric stimulation technology (BEST) platform (Tennant Biomodulator® PRO, AVAZZI A, Inc) during the entire length of stay in hospital. The device will be provided by the research staff.

We will assess incidence of neuropathy and myopathy during hospital discharge or 4 weeks, whichever comes first. Neuropathy severity will be quantified using vibratory perception threshold (VPT) test. Myopathy will be assessed by measuring changes in calf muscle circumference, weight change from pre-hospital admission, and sEMG. In addition, we will determine weakness using foot dynamometer and a validated frailty meter. Length of hospital stay and MAE (documented via electronic health record) will be tracked for planning of future studies. Both extremities will have all measurements and 1 hour electrical stimulation therapy at baseline. Daily treatment will be performed up to 3 times per day, but no more than 1 hour in total.

Daily electrical stimulation will be administered by a nurse/staff involved in the hospital care. A chart will be signed to register each therapy performed and will include a log of day and time of device application.

Both electrical stimulation and EMG devices will have disposable pads, after usage they will be discarded. For the Devices

they will be placed inside a plastic bag that will be disposed inside the room before exiting and sanitized (wipes) based upon hospital protocols.

The researchers will take digital photographs /videos throughout the study. This is done using a special camera for tissue oxygen detection and visual images. This method is non invasive and does not cause any harm to the patient. **We will blur the face out in the photographs/videos. We will only use videos and photos for scientific presentations or scientific publications.

Phase II:

Patients will begin the study after being diagnosed with neuromyopathy due to prolonged hospitalization for COVID-19. This will be performed by a critical care and pulmonary specialist at the BCM COVID-19 Clinic.

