The protocol will consist of 4 weeks of lower-extremity electrical stimulation. Opposite to our initial study, this modality will consist of home-based therapy, meaning that the patient will take the device home and attend the clinic once a week for screening and assessment of therapy.

The protocol will be performed as the following description: This trial will have 20 patients divided in two groups. Group 1 (intervention, n=10): Will receive an active Tennant Biomodulator Group 2 (control, n=10): Will receive an inactive Tennant Biomodulator This study will consist of 5 visits total and one phone interview 12 weeks after baseline for both groups. The patient will be compensated \$50 per visit (total \$250), with free parking. Payment will only be available for subjects who participate in Part II.

During the first and last visit, the research staff will turn the Tennant Biomodulator PRO® on for one hour and measure any changes in muscle strength, endurance, and blood flow after the therapy. Once the first visit is over, the patient will take the Tennat Biomodulator® home and will be instructed to turn it on for one hour every day for four weeks.

The visits in-between will be performed in the following order: 1) Questionnaires (pain, weakness, sleep, quality of life, frailty, depression, life and space, beck anxiety scale, Katz-daily living) 2) Musculoskeletal assessments (non-invasive surface electromyography, vibration perception threshold) 3) Vascular assessments (non-invasive Near infra-red spectroscopy)

After 4 weeks, the patients will turn back the device to the research staff.

The supervision of this study will be by pulmonary care specialists, and the location will be at the recently open COVID-19 clinic at Baylor College of Medicine.

Section G: Sample Size/Data Analysis

G1. Sample Size

How many subjects (or specimens, or charts) will be used in this study?

Local: 40 Worldwide: 40

Please indicate why you chose the sample size proposed:

Sample size is convenient and selected based on available resources to demonstrate feasibility and the proof of concept effectiveness of EE therapy for COVID-19 patients admitted to ICU and post-ICU. We plan to recruit 40 eligible subjects.

G2. Data Analysis

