The risk to participants of this study is considered to be minimal in a controlled environment with an attendant present. This research routine will not place subjects at higher risk than normal activities of daily living, and no more risk of harm or discomfort is associated with these tests than the discomfort normally incurred while performing normal muscle stretching. Subjects will be allowed rest time between trials as needed. The EMG device will detect level of fatigue and based on that we will determine the length of the sessions.

The devices and technology is completely non-invasive, safe, non-toxic and non-ionizing. The potential risks to subject are minimal. However, like any battery powered systems, there is a minimum risk of sensor malfunctioning. In addition, the study devices are not waterproof, and although they use a low powered battery (similar to a cellphone battery), in order to avoid any risk of shock the monitor should not be submerged or saturated with fluids during operations or cleaning. It does not emit any radiation to the human body, and does not offer any significant risk to the subject.

Subjects may experience mild discomfort from the sensor on their legs. We will inform the subject to please notify the investigators if the sensor is uncomfortable.

All information we will collect about the subject will be stored in a secure location and coded in a way to maintain confidentiality. Only study personnel will have access to their records. Data collected during the study may be published and made publicly available. Data may also be shared with other research groups. However, data that could in any way identify them will not be made public or shared.

Some of potential risks of using TENS therapy could be: * Skin related discomfort, such as tingling * Skin reaction to adhesive patch.

If the tingling sensation is too intense for the participant, they have the ability to reduce the intensity for their best level of comfort.

H2. Data and safety monitoring plan

Do the study activities impart greater than minimal risk to subjects?
No

H3. Coordination of information among sites for multi-site research

Is the BCM Principal Investigator acting as the SPONSOR-INVESTIGATOR for this multi-site research?
No or Not Applicable

Is BCM the COORDINATING CENTER for this multi-site research?
No or Not Applicable

Section I: Potential Benefits

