Do anticipated benefits outweigh potential risks? Discuss the risk-to-benefit ratio.

This study brings no more than minimal risk to subjects as it only involves a non-invasive device. There are some risks associated with lack of comfort from EE, skin allergy to the EE sticky patches that are used for delivering EE therapy, risk associated with electrical mal-function of EE, and other unknown risks. All EE devices will be checked before any use to minimize the risk associated with electrical malfunction. All EE devices are FDA approved for the purpose of pain reduction. However, these devices have not been used before for purpose of managing COVID-19 side effects like the purpose of this study. Although there is no direct benefit for participating in the study, their participation may help the investigators design a practical assessing method to identify the impact of Neuromyopathy in the hospital (inpatient) setting.

Section J: Consent Procedures

J1. Waiver of Consent

Will any portion of this research require a waiver of consent and authorization?

No

J1a. Waiver of requirement for written documentation of Consent

Will this research require a waiver of the requirement for written documentation of informed consent?

No

J2. Consent Procedures

Who will recruit subjects for this study?

PI

PI's staff

Describe how research population will be identified, recruitment procedures, any waiting period between informing the prospective participant and obtaining consent, steps taken to minimize the possibility of coercion or undue influence and consent procedures in detail.

Subjects will be recruited from the hospital. They may get some referrals from other collaborators. In order to recruit or identify subjects, we will screen our patient charts for eligible subjects. The COI will identify eligible subjects and alert the coordinator. The coordinator will review all the details of the study with the subject and/or their family. If the subject agrees to participate in the study, they will be screened and then enrolled into the study.

We will be conducting the study during the first days of their stay in the hospital, in case the patient is not able to consent we will ask for consent from their legal authorized representative. The legal representative will be consented the same way the patient would but over the phone by stating the procedures/ benefits/ risks and ask questions.

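### The minimal-risk statement in H1 does not fit home sessions or patients who cannot respond, and nothing described systematically records the device risks the protocol names

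*Protocol*

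**What the plan says.** Protocol section H1 opens with "The risk to participants of this study is considered to be minimal in a controlled environment with an attendant present". On stimulation that is too strong it says: "If the tingling sensation is too intense for the participant, they have the ability to reduce the intensity for their best level of comfort". On sensor discomfort: "We will inform the subject to please notify the investigators if the sensor is uncomfortable". Section H2 answers No to greater than minimal risk, and no monitoring plan follows. The risk-benefit discussion in Section I gives a separate ground: "This study brings no more than minimal risk to subjects as it only involves a non-invasive device".

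The settings are these:

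- **Phase I (F1, F2 Aim 2, J2, J6).** Inpatients are enrolled, including adults without capacity to consent. A nurse or other staff member gives the daily session. F1 also says "we are looking to reduce the interaction with staff, the device will be placed with no additional requirements". The treatment record is described as follows: "A chart will be signed to register each therapy performed and will include a log of day and time of device application".
- **Phase II (F2, J2).** Here "the patient will take the device home and attend the clinic once a week for screening and assessment of therapy". The device is used for an hour a day for four weeks, and staff switch it on only at the first and last of five visits. Participants must be alert.

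H1 and Section I name the device risks: tingling or discomfort, skin reaction to the patches, electrical malfunction, and unknown risks. The only safety outcome listed is major adverse events, taken from the health record. The examples given are deep vein thrombosis, cardiovascular events and death. The SAP contains no safety analysis.

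**The concern.** The attendant condition in H1 describes a setting that is not the Phase II setting and is not assured in Phase I. The comfort measures need a patient who can feel, judge and act. A Phase I patient who cannot respond can neither turn the device down nor complain, and the documents do not say who is responsible for intensity in that case.

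The statistical consequence is in the data. If skin reactions, discomfort and malfunctions are not asked about, few or no reports could mean good tolerability or simply no collection, and the two cannot be told apart. Section I says the device has not been used before for managing COVID-19 side effects, so tolerability is one of the things a pilot can usefully report. Phase II, as F2 describes it, compares active with inactive devices and could give a controlled look at tolerability. That is lost if the items are not collected in both groups.

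**Working it through.** The plan has no figure to reproduce. The sample size of 40 (20 + 20) is a convenience number with no event rate behind it. The check is therefore a comparison of sections, followed by an illustration of what counting events could show.

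**1. Does the attendant condition hold?**
- Phase II home sessions: no. Active group in F2: 10 patients × 28 days = 280 sessions at most. If the first-visit and last-visit sessions count among the 28, it is 10 × 26 = 260.
- Phase I: uncertain. Staff give the session, but presence throughout is neither stated nor denied, and F1 aims to reduce contact.

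**2. Do the comfort measures work?**
- Phase II: yes in principle, because participants are alert and can adjust or report.
- Phase I: not for patients unable to respond. F1 says only that some cannot consent, so the share is unknown.

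**3. Do the other stated safeguards record the named risks?**
- Device check before use (Section I): aimed at malfunction. No record is described, and who does it at home is not stated.
- Session length set by EMG fatigue, and rest time (H1): concerns fatigue. No EMG at home is described.
- Exclusion of implanted electronics and active wound infection (F1): acts at entry only.
- Weekly Phase II attendance (F1, F2): a natural collection point, but the listed items are questionnaires, surface EMG, vibration threshold and near-infrared measurement. The pain questionnaire is not tied to the device.
- Critical information sent to the medical record (J2): selective, not systematic.

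None is described as a routine record of skin reaction, stimulation discomfort or malfunction.

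**4. What would a count be worth?** For zero events in n patients who were actively asked, the one-sided 95% upper bound is 1 − 0.05^(1/n):
- n = 10 (Phase II active group): 1 − 0.05^(1/10) = 25.9%.
- n = 20 (Phase I, all stimulated as F1 states): 1 − 0.05^(1/20) = 13.9%.

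The chance of seeing at least one event is 1 − (1 − p)^n. The documents give no rate, so p = 5% and 10% are assumptions:
- n = 10: 40% and 65%.
- n = 20: 64% and 88%.

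Asking would be informative even at this size, although zero events could not show that the risk is negligible. Without asking, none of these figures applies.

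**The case against.** The strongest reply is that the protocol does more than rely on an attendant and on patient complaint. It has device checks, EMG-guided session length, exclusions and weekly visits, and it rests minimal risk separately on the device being non-invasive. This stands. A reader might infer from H1 that the attendant and the patient's own action are the only safeguards, or that the H2 answer depends on them alone. The documents do not support either reading.

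Three further points also stand:

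- Phase I sessions are staff-administered and Phase II participants are alert. It would be wrong to say that both H1 conditions fail in both phases.
- A reader might infer that device events are recorded nowhere. The chart is said to include day and time, which does not exclude other fields. The list of major adverse events is open-ended. Participants are asked to speak up, and case report forms are not in the documents. The supportable statement is that no systematic capture is described.
- The zero-event bounds are not evidence of harm. The n = 20 bound also assumes every Phase I patient is stimulated, whereas the SAP refers to a control and an intervention group without giving sizes. If 10 of the 20 were controls, the bound would return to 25.9%.

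The objection does not supply a collection point for the three named risks. Nor does it show how a patient unable to respond is covered by a measure that requires a response.

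**Conclusion.** The concern holds in a limited form. The H1 attendant wording does not describe Phase II home use (up to 280 active-group sessions, or about 260 on the other count) and is not assured throughout Phase I sessions. The participant-dependent comfort measures cannot protect Phase I patients who are unable to respond, a group of unstated size. No described outcome, log field, visit item or SAP analysis systematically captures patch reaction, stimulation discomfort or malfunction, so a zero count would support no safety statement.

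This rests on the protocol and SAP alone; case report forms, if they contain these items, would narrow it. It does not show that the device is unsafe, that the minimal-risk rating is wrong, or that the efficacy analysis is affected. It should be corrected before the pilot's safety results are interpreted.

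**What to change.** 1. Add three fields to the chart already signed at each Phase I session, completed when the pads come off: skin reaction at the electrode site, sign or report of discomfort, and device malfunction.
2. Ask the same three items at each of the five existing Phase II visits, in both groups.
3. Add to the SAP a table of these items by group and phase, with the number of patients and of sessions or visits at which the items were completed. A zero then has a denominator.
4. Reconcile F1 (Phase I), F2 (Phase I Aim 2 and Phase II), H1 and the risk-benefit text in Section I. The risk statement should describe the two actual settings, a patient unable to report and home use without an attendant, and should say who is responsible for intensity when the patient cannot adjust it. What that arrangement should be is for the investigators and the ethics board. The H2 answer may remain No if it is justified for those settings.

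The cost is about a minute of staff time per session or visit, some redrafting, and possibly a less favourable-looking safety table. No new visit is needed.
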